## II. Indication

### 1. Inclusion Criteria

- (1) Age 40-80 years;
- (2) First-onset stroke patients;
- (3) Patients diagnosed with cerebral infarction or hemorrhage through CT or MRI;
- (4) Signed informed consent form by the patient and their family;
- (5) Stable physiological parameters;
- (6) Stroke occurred within the last 12 months;
- (7) Patients with unilateral hand function impairment caused by the stroke;
- (8) Upper limb muscle tone (Modified Ashworth Scale, MAS) less than 3 points;
- (9) Able to follow two-step commands.

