## VI. Study Design

- Duration of Treatment

- A. The experiment for establishment of therapeutic environment.

Participants in the experiment for establishment of therapeutic environment underwent 1-3 evaluations. During this experiment, repetitive Transcranial Magnetic Stimulation (rTMS) was employed for brain modulation, involving two sets of stimuli. Each set consisted of initially administering continuous Theta Burst Stimulation (cTBS) to suppress the healthy side (approximately 600 pulses), followed by intermittent Theta Burst Stimulation (iTBS) to enhance the lesion side (600 pulses), totaling approximately 4 minutes (around 1200 pulses). The intensity of iTBS and cTBS is 80-120% of Motor Threshold.

Patients receiving rTMS treatment concurrently underwent machine-assisted bilateral upper limb training. During treatment sessions, patients were instructed to repeatedly perform grasping-opening tasks or engage in bilateral upper limb activities involving simultaneous shoulder and elbow movements while counting down loudly from 300. Upon completion of all training sessions, patients and therapists were required to complete usability and satisfaction analyses to evaluate equipment usability and operational satisfaction.

- B. The experiment for evaluation of therapeutic effects.

Patients will be divided into three groups: a Control group, an rTMS group, and an rTMS+BT group. Each group will receive a 65-minute treatment session, administered once every two days, totaling 10 sessions and completing the entire course within 20 days.

Control group: only received traditional rehabilitation training for 50 minutes and self-stretching training (15 minutes); rTMS group: received rTMS intervention (15 minutes) and 50 minutes of traditional rehabilitation training; rTMS+BT group: received rTMS intervention (15 minutes) along with BT meanwhile and 50 minutes of traditional rehabilitation training.

- Number of Planned Patients

72 participants are expected to be recruited in the trial.

- Investigational Product

1. Robot-assisted palm and finger rehabilitation device

Device name: "RM" Wearable Powered Hand Rehabilitation Device (Non-Sterile)

Manufacturer: Rehabotics Medical Technology Corporation

2. Bilateral proximal/distal upper limb training platform

- (1) The name of proximal upper limb training device: Non-powered upper limb proximal training platform

Manufacturer: Rehabotics Medical Technology Corporation

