- (2) The name of distal upper limb training device: Non-powered upper limb distal training equipment

Manufacturer: developed equipment by the Rehabilitation Department of Chang Gung Hospital

3. Repetitive transcranial magnetic stimulation (rTMS)

Device name: Repetitive transcranial magnetic stimulation (rTMS)

Manufacturer: Apollo Powermag 100, Mag & More, Germany.

- Endpoints

The primary endpoint was evaluated through the Fugl-Meyer Assessment, while secondary endpoints encompassed various measures, including the Modified Ashworth Scale (MAS), Manual Muscle Testing (MMT) for the upper extremity, Action Research Arm Test (ARAT), Brunnstrom Recovery Stage, Instrumental Activities of Daily Living Scale (IADLs). Additionally, participants and therapists responded to the System Usability Scale (SUS) questionnaire, and a Satisfaction questionnaire was administered.

- Criteria for Evaluation

1. Inclusion Criteria

- (1) Demographics and baseline characteristics of the participants were all available.

- (2) Participants completed all treatment sessions.

- (3) Functional assessments of the upper limb were performed at multiple time points: prior to, immediately after, and at 1 and 3 months follow-ups, without any omissions.

- (4) Both participants and therapists completed the System Usability Scale (SUS) questionnaire and the Satisfaction questionnaire.

2. Exclusion Criteria
  - (1) Participants with unforeseen psychological issues or significant changes in health conditions to prevent interference with the analysis.
  - (2) Participants using non-study-related medications that could potentially interfere with the outcomes.

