### ● Statistical Methods

Detailed demographic and medical history records are documented for each subject, including age, gender, time of stroke onset, location of stroke, and types of stroke. The clinical assessment will be conducted by a licensed occupational therapist with experience in treating neurological conditions. Clinical assessment results are being compared between groups using a student-t test. Pre and post-training within each group are being assessed using one-way ANOVA to determine improvement. One-way ANOVA is employed for inter-group comparisons, followed by post-hoc tests. If the data do not follow a normal distribution, non-parametric statistical methods are applied. Correlation analysis is used to explore relationships between clinical assessment results and various factors. Quantitative data are presented as (Mean±SEM), and a 95% confidence interval ( $p<0.05$ ) is considered statistically significant.

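### The normality rule lets the observed outcomes decide whether FMA is compared on means or on ranks, without fixing the visit, score form or check it applies to

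*Protocol*

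**What the plan says.** All statements are in section VI (Study Design) of the protocol unless noted.

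- **Default tests (Statistical Methods).** Two between-group tests are named: "Clinical assessment results are being compared between groups using a student-t test" and "One-way ANOVA is employed for inter-group comparisons, followed by post-hoc tests". Within groups, "Pre and post-training within each group are being assessed using one-way ANOVA to determine improvement".
- **Switch (Statistical Methods).** "If the data do not follow a normal distribution, non-parametric statistical methods are applied". No normality criterion and no replacement test is named. Quantitative results are to be shown as mean and SEM, with no other summary for the case where a rank test is used.
- **Endpoint (Endpoints).** "The primary endpoint was evaluated through the Fugl-Meyer Assessment". Neither a primary visit nor a score form (post-treatment value or change) is given.
- **Visits (Criteria for Evaluation).** Upper-limb function is assessed "prior to, immediately after, and at 1 and 3 months follow-ups, without any omissions", so there are three post-treatment visits.
- **Groups and size.** "Patients will be divided into three groups: a Control group, an rTMS group, and an rTMS+BT group", with 72 participants planned in total.
- **Population (section II, Inclusion Criteria).** "Stroke occurred within the last 12 months". The criteria set no FMA range at entry.

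**The concern.** The switching sentence makes the method for the primary endpoint a function of the outcomes, and it leaves *data* undefined. The word could mean raw scores, changes or residuals; all arms together or each arm; each visit or all visits. Each reading complies with the protocol, and different readings can call for different tests on the same trial.

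A switch also changes the question. The t-test and ANOVA compare mean FMA. The usual rank tests compare the ordering of scores, and their p-value does not test the difference between the displayed means. A trial could follow the protocol to the letter and report ANOVA after treatment, a rank test at 1 month and ANOVA again at 3 months.

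Patients up to a year after stroke with no set FMA range may well give a broad or skewed distribution. The documents provide no data on this, so it has to be assumed.

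**Working it through.** The protocol attaches no figure to this rule, so there is none to reproduce. The check asks how often the rule changes the method, and whether that matters.

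**Inputs from the protocol:** three groups, 72 participants, three post-treatment visits, significance at 0.05.

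**Assumptions:** equal allocation with all 72 in the treatment-effect experiment, so 72/3 = 24 per arm; FMA as the upper-extremity score, 0–66; normality judged by Shapiro-Wilk at 0.05; Kruskal-Wallis as the replacement for ANOVA.

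**1. Exactly normal data.** If the rule fires when any one of three arms is flagged, the chance of a needless switch is 1 − 0.95³ = 0.143 (simulated 0.143, 10,000 trials). A single pooled check switches in about 5%. The readings diverge even when nothing is wrong with the data.

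**2. Main simulation (2,000 trials per row).** Baselines were near-normal (mean 33, SD 9), flat (66 × Beta(1.1, 1.1)) or right-skewed (66 × Beta(1.2, 2.5)). Gains were 6, 7 and 8 points at the three visits. Person and visit noise each had SD 3, and scores were rounded and limited to 0–66. Group effects were nil or 0/3/6 points. The pooled check used all 72 raw scores; the per-arm check fired if any arm was flagged. All columns except the visit comparison refer to the first post-treatment visit.

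| Baseline, effect | Pooled check chooses ranks | Test family differs between visits | Pooled and per-arm checks choose different tests | Those checks differ on significance |
|---|---|---|---|---|
| Near-normal, nil | 4.6% | 10.0% | 13.0% | 0.2% |
| Near-normal, 0/3/6 | 4.2% | 9.9% | 13.2% | 0.8% |
| Flat, nil | 95.4% | 5.1% | 31.6% | 0.1% |
| Flat, 0/3/6 | 98.4% | 1.5% | 15.6% | 0.2% |
| Skewed, nil | 67.0% | 32.3% | 32.1% | 0.6% |
| Skewed, 0/3/6 | 58.3% | 34.2% | 28.6% | 1.4% |

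With no effect, the two-stage rule rejected in 0.042–0.054 of trials. The Monte Carlo standard error is √(0.05 × 0.95/2000) = 0.005. ANOVA with no normality check rejected in 0.042–0.056 on raw scores and 0.044–0.048 on changes.

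**3. Other assumptions.**
- With bell-shaped, flat or U-shaped baselines, recovery declining with time since stroke, and pooling of within-arm residuals (1,500 trials per setting), the family differed between visits in 7–67% of trials. The two checks chose different tests in 12–33%, and the rule's size was 0.038–0.055. ANOVA and Kruskal-Wallis disagreed on significance in 0.9–2.8% of null trials and up to 8.8% with an effect.
- A further run at 24 per arm gave 8–34% between visits, 12–35% between checks, size 0.047–0.061, and a changed verdict in about 0.3–1.3%.

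Taken together: visits 2–67%, checks 12–35%, size 0.038–0.061, verdict changed 0.1–1.4%.

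**4. Raw score versus change.** In the step 2 simulation, checking raw scores rather than changes led to a different test in 10% (near-normal), 89–94% (flat) and 58–65% (skewed) of trials. Power was 0.12–0.43 on raw scores and 0.95–0.995 on changes. That power gap comes mainly from the unfixed form of the endpoint, not from the normality rule.

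**5. Unequal variances, which the rule does not look for.** True error of Student's t at nominal 0.05:

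| Arms | Larger SD in | SD ratio 1.5 | SD ratio 2 |
|---|---|---|---|
| 24 v 16 | smaller arm | 0.070 (Welch 0.050) | 0.086 (Welch 0.052) |
| 24 v 16 | larger arm | 0.036 | 0.030 |

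With 24 v 24 and SD ratio 1.5–2 it was 0.048–0.053. With 24 v 20 and ratio 1.5 it was 0.059. Neither the imbalance nor the SD ratio comes from the documents.

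**The case against.** The strongest reply is that the document is a synopsis and the SAP is not shown. Which normality check is used, on what quantity, and which rank test follows are matters often left to the SAP, and the 12–35% measures only that unstated detail. This stands in part: the missing detail alone would not be a finding. But the protocol states the switch itself. An SAP that follows it can define the trigger, yet the choice between means and ranks would still depend on the outcomes.

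The second reply is that little changes in practice. Error is near nominal and the two checks almost always reach the same verdict. This stands, and it limits the severity.

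A reader might infer more, but the documents do not support it:

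- *The choice is made on unmasked data.* The protocol does not say whether the person checking normality knows the allocation, and a pooled check needs no labels.
- *Raw scores are checked rather than residuals.* The sentence does not say which.
- *Switching loses adjustment for pre-treatment FMA.* The default t-test and one-way ANOVA do not adjust either, so the rule does not cause that loss.
- *Visits can no longer be compared.* Group means in points remain available at every visit; only the tests differ in kind.
- *Student's t has 7–9% error here.* That needs an assumed 24 v 16 split with the larger SD in the smaller arm. Reversing the direction makes the test conservative.

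**Conclusion.** The point holds at low to moderate severity. The protocol lets the distribution of the outcomes choose between t-test/ANOVA and an unnamed non-parametric test for FMA, and it ties that choice to no visit, score form or level of checking. The frequencies rest on 24 per arm, Shapiro-Wilk at 0.05, a 0–66 score and assumed score shapes. The wide 2–67% range for visits shows how far the result depends on those shapes, so no single value should be quoted as the expected one.

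The cost is in interpretation: the quantity tested is settled by the data, the displayed means may not be what the p-value tests, and the analyst is left a choice that serves no purpose. The calculations do not support reading the rule as a source of false positives, or as an easy way to turn a negative result positive. The Student-versus-Welch comparison is only a secondary reason for robust standard errors, since it depends on the assumed imbalance and the direction of the variance difference.

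**What to change.** Delete the switching sentence as it applies to FMA. State one analysis, used at every post-treatment visit whatever the distribution looks like: a linear model for FMA in points with group and pre-treatment FMA as terms, HC3 standard errors, and each between-group difference with its 95% confidence interval. Let this replace both default between-group tests for FMA, so that the section names a single method. With pre-treatment FMA in the model, post-treatment score and change give the same between-group difference, which also removes the choice in step 4. Which visit is primary still has to be stated separately.

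Name one rank-based analysis as a sensitivity analysis that cannot replace the main result. Assign ordinal or rank methods to MAS, MMT and Brunnstrom in advance because of their scales, and name the method for ARAT and IADLs in advance too.

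The chance that the method changes between visits or readings then becomes zero by construction. The change costs wording only. The downside is a small possible loss of power if FMA is heavily skewed, a case in which the rank-based sensitivity analysis would be informative. The error rates for ANOVA without a normality check in step 2 suggest that a mean comparison is safe at this size under the assumed shapes; the HC3 model itself was not simulated.

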### ● Duration of the Study

The study is scheduled to span a total of three years, commencing on August 1st, 2024, and concluding on July 31st, 2027.

### ● End of Study

In summary, this three-year study, conducted from August 1, 2024, to July 31, 2027, focuses on establishing an integrated approach using rTMS with BT for treating upper limb hemiparesis in stroke patients. The research credits the collaboration of participants, the medical team, and supporting institutions. We are optimistic that the insights gained will play a crucial role in advancing the field of stroke rehabilitation.
